1. AMENDMENTS FROM PREVIOUS VERSION(S)

None.

2. INTRODUCTION

PF-07321332 is a potent and selective inhibitor of the SARS-CoV-2 3CL protease that is currently being developed as an oral treatment of COVID-19. Ritonavir is a strong CYP3A4 inhibitor being used to inhibit the metabolism of PF-07321332 in order to increase plasma concentrations of PF-07321332 to values that are anticipated to be efficacious.

The purpose of the study is to evaluate the effect of the strong CYP3A4 inhibitor, itraconazole, on the PK of PF-07321332 in healthy participants. Results from this study will provide guidance for dosing recommendations with concomitant medications during Phase 3 development and further establish the safety margins of PF-07321332/ritonavir.

2.1. Study Design

This is a Phase 1, open-label, 2-period, fixed sequence crossover study to estimate the effect of the strong CYP3A4 inhibitor, itraconazole, on the PK of PF-07321332 and ritonavir in healthy participants. The study will consist of 2 treatments: multiple oral doses of 300 mg PF-07321332/100 mg ritonavir alone and multiple oral doses of 300 mg PF-07321332/100 mg ritonavir in combination with itraconazole. A total of approximately 12 healthy male and/or female participants will be enrolled into the study to ensure at least 9 participants will complete the study. The treatment will consist of a single fixed sequence. Participants who discontinue from the study for non-safety reasons may be replaced at the sponsor's discretion in collaboration with the Investigator.

Healthy participants will be screened to determine eligibility within 28 days prior to study treatment. Medical history and results of physical examination, physical measurements, vital signs, 12-lead ECGs, and clinical laboratory evaluations will determine eligibility.

In Period 1, each enrolled participant will receive 300 mg PF-07321332/100 mg ritonavir administered orally, q12h for 5 doses, from Day 1 morning to Day 3 morning. Serial PK samples will be collected up to 48 hours post the 5th dose on Day 3 to establish baseline exposure of PF-07321332. PK samples will also be collected predose the morning and evening doses of PF-07321332/ritonavir on Day 2 to confirm steady state.

Period 2 will begin on Study Day 5 (referred to as Period 2, Day 1). Participants will receive 200 mg itraconazole, administered orally, QD, on Period 2, Days 1 through 8, inclusive. On Days 4, 5, and 6, participants will receive 300 mg PF-07321332/100 mg ritonavir administered orally, q12h for 5 doses, from Period 2, Day 4 morning to Day 6 morning.

Following the final administration of PF-07321332/ritonavir on the morning of Day 6, participants will undergo serial PK sampling up to 72 hours post the last dose. PK samples will also be collected predose the morning and evening doses of PF-07321332/ritonavir on Day 5 to confirm steady state. Participants will be discharged from the CRU on Period 2, Day 9 following completion of all assessments.

If a participant has any clinically significant, study related abnormalities at the conclusion of a scheduled inpatient portion of the study, the Pfizer medical monitor (or designated representative) should be notified and the participant may be asked to remain in the CRU until such abnormalities are deemed not clinically significant, or it is safe for outpatient follow-up.

A safety follow-up call will be made to participants approximately 28 to 35 days from administration of the final dose of study intervention. The total planned duration of participation, from the Screening visit to the last Follow-up phone call, is approximately 10 weeks.

Study Schema:

Screening	Treatment		Follow-Up
	Period 1	Period 2	
	Period 1, Day -1 to Day 4	Period 2, Day 1 to Day 9	
	(Reference) PF-07321332/ritonavir 300 mg/100 mg q12h x 3 days (total of 5 doses)	(Test) Itraconazole: 200 mg qd for 8 days + PF-07321332/ritonavir 300 mg/100 mg q12h x 3 days starting on Day 4 (total of 5 doses)	
Study Days	Days -28 to -2	Days -1 to 4	Days 5 to 13
			Days 28 to 35

2.2. Study Objectives

2.2.1. Primary Objective

- *To estimate the effect of multiple doses of itraconazole on the PK of PF-07321332 following multiple doses of PF-07321332/ritonavir.*

2.2.2. Secondary Objectives

- *To evaluate the safety and tolerability of PF-07321332/ritonavir in healthy participants in the absence and presence of multiple doses of itraconazole.*
- *To characterize the PK of PF-07321332 following multiple doses when PF-07321332/ritonavir is administered alone or with itraconazole in healthy participants.*

CCI

3. INTERIM ANALYSES, FINAL ANALYSES AND UNBLINDING

No formal interim analysis will be conducted for this study. As this is an open-label study, the sponsor may conduct unblinded reviews of the data during the course of the study for the purpose of safety assessment, facilitating PK/PD modeling, and/or supporting clinical development.

4. HYPOTHESES AND DECISION RULES

4.1. Statistical Hypotheses

There are no statistical hypotheses for this study.

4.2. Statistical Decision Rules

There are no statistical decision rules.

5. ANALYSIS SETS

5.1. Enrolled/Randomly Assigned to Study Intervention

"Enrolled" means a participant's, or their legally authorized representative's, agreement to participate in a clinical study following completion of the informed consent process and screening. Potential participants who are screened for the purpose of determining eligibility for the study, but do not participate in the study, are not considered enrolled, unless otherwise specified by the protocol. A participant will be considered enrolled if the informed consent is not withdrawn prior to participating in any study activity after screening.

5.2. Pharmacokinetic (PK) Analysis Set

5.2.1. Concentration Analysis Set

All participants who take at least 1 dose of study intervention and in whom at least 1 concentration value is reported.

5.2.2. Parameter Analysis Set

All participants who take at least 1 dose of study intervention and in whom at least 1 of the PK parameters of interest are reported.

5.3. Pharmacodynamic Analysis Set

None.

5.4. Safety Analysis Set

All participants who take at least 1 dose of study intervention. Participants will be analyzed according to the product they actually received.

5.5. Other Analysis Sets

None.

5.6. Treatment Misallocations

All analyses will be performed on an “as-treated” basis and will not include data from participants who are randomized but not treated.

If a participant takes a treatment that is not consistent with the treatment they are randomized to, for example takes a treatment out of sequence or takes the same treatment twice, then they will be reported under the treatment that they actually receive for all safety, PK and pharmacodynamic analyses, where applicable.

5.7. Protocol Deviations

Participants who experience events that may affect their PK profile (eg, lack of compliance with dosing) may be excluded from the PK analysis. At the discretion of the pharmacokineticist a concentration value may also be excluded if the deviation in sampling time is of sufficient concern or if the concentration is anomalous for any other reason.

A full list of protocol deviations will be compiled and reviewed to identify major and minor deviations prior to database closure.

5.7.1. Deviations Assessed Prior to Randomization

At Screening, the investigator will assess participants against the inclusion and exclusion criteria as set out in Sections 5.1 and 5.2 of the protocol.

5.7.2. Deviations Assessed Post-Randomization

A full list of protocol deviations for the study report will be compiled prior to database closure. Any significant deviation from the protocol will be reviewed prior to database closure and a decision taken regarding evaluation for each analysis population.

6. ENDPOINTS AND COVARIATES

6.1. Efficacy Endpoint(s)

None.

6.2. Safety Endpoints

The following data are considered in standard safety summaries (see protocol for collection days and list of parameters):

- *adverse events,*
- *laboratory data,*
- *vital signs data,*
- *ECG results.*

6.2.1. Adverse Events

An adverse event will be considered a Treatment-Emergent Adverse Event (TEAE) if the event started during the effective duration of treatment. All events that start on or after the first dosing day and time/start time, if collected, but before the last dose plus the lag time (28 days) will be flagged as TEAEs. The algorithm will not consider any events that started prior to the first dose date. Any events occurring following start of treatment or increasing in severity will be counted as treatment emergent.

Events that occur in a non-treatment period (for example, Follow-up) will be counted as treatment emergent and attributed to the previous treatment taken.

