4.3. Justification for Dose

This study is designed to estimate the effect of multiple dose administration of 200 mg daily itraconazole on multiple dose PK of PF-07321332 and ritonavir. A dose of 300 mg PF-07321332, pharmacokinetically enhanced with 100 mg ritonavir, to be administered q12h for 5 doses with and without itraconazole will be used. This dose is the intended therapeutic dose to be evaluated in Phase 2/3 studies and is appropriate considering concomitant administration of PF-07321332 with ritonavir provides near maximal CYP3A4 inhibition and the addition of itraconazole is not expected to result in a significant increase of systemic exposures of PF-07321332. **CC1**

An oral dose of itraconazole 200 mg solution administered QD for 8 days will be used to provide a substantial degree of CYP3A4 inhibition. Doses greater than 200 mg are not

expected to provide any additional CYP3A4 inhibition.⁷ PF-07321332/ritonavir will be administered under fasting conditions approximately 1 hour after itraconazole administration on Period 2, Days 4, 5, and 6 to maximize itraconazole systemic exposures and CYP3A4 inhibition. Itraconazole will continue to be administered on Period 2, Days 7 and 8 to maintain maximal CYP3A4 inhibition until completion of PK sampling.

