8.2. Statistical Analyses

Natural log transformed parameters (AUC_{tau} and C_{max}) of PF-07321332 will be analyzed using a mixed effect model with treatment as fixed effect and participant as a random effect. Estimates of the adjusted mean differences (Test-Reference) and corresponding 90% CIs will be obtained from the model. The adjusted mean differences and 90% CIs for the differences will be exponentiated to provide estimates of the ratio of adjusted geometric means (Test/Reference) and 90% CI for the ratios. PF-07321332/ritonavir administered alone will be the Reference treatment and PF-07321332/ritonavir co-administered with itraconazole will be the Test treatment. Additionally, the aforementioned analysis will be performed for the same PK parameters of CCI [REDACTED] and is intended to not be included in the clinical study report.

Residuals from the model will be examined for normality and the presence of outliers via visual inspection of plots of residuals vs predicted values and normal probability plots of residuals but these will not be included in the clinical study report. If there are major deviations from normality or outliers then the effect of these on the conclusions will be investigated through alternative transformations and/or analyses excluding outliers.

Justification for any alternative to the planned analysis will be given in the report of the study.

The plasma concentrations of PF-07321332 [REDACTED] will be listed and descriptively summarized by analyte, nominal PK sampling time and treatment.

Table 1. PK Parameters to be Summarized Descriptively by Analyte and Treatment

Parameter	Summary Statistics
AUC _{tau} , AUC _{last} , C _{max} , CL/F*, V _Z /F*	N, arithmetic mean, median, cv%, standard deviation, minimum, maximum, geometric mean and geometric cv%.
T _{max}	N, median, minimum, maximum.
t _{1/2}	N, arithmetic mean, median, cv%, standard deviation, minimum, maximum.

*: if data permit

Box and whisker plots for individual participant parameters (AUC_{tau}, AUC_{last} and C_{max}) will be presented by analyte and treatment and overlaid with geometric means.

Supporting data from the estimation of t_{1/2} and AUC_{tau} will be listed by analyte and treatment: terminal phase rate constant (k_{el}); goodness of fit statistic from the log-linear regression (r²); and the first, last, and number of time points used in the estimation of k_{el}. This data may be included in the clinical study report.

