8.3. Safety Analysis

All safety analyses will be performed on the safety population. A set of summary tables split by treatment will be produced to evaluate any potential risk associated with the safety and toleration of administering study treatments.

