8.3.3. Discontinuation(s)

Participant discontinuations, temporary discontinuations or dose reductions due to adverse events will be detailed and summarized by treatment.

Data will be reported in accordance with the sponsor reporting standards.

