8.3.4. Adverse Events

Adverse events will be reported in accordance with the sponsor reporting standards by treatment.

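### The by-treatment TEAE summary sets about 4 days of Reference against 8 inpatient days, and at most 35 days in total, of Test, because follow-up and itraconazole-only days both fall under Test

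*SAP*

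**What the plan says.** SAP 6.2.1 flags events as TEAEs from the first dose until 28 days after the last dose. It then adds: "Events that occur in a non-treatment period (for example, Follow-up) will be counted as treatment emergent and attributed to the previous treatment taken".

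Three other statements decide how that rule works in this trial:

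- **Sequence.** SAP 2.1: "The treatment will consist of a single fixed sequence". Reference is always Period 1 and Test always Period 2.
- **What counts as Test.** The schema in SAP 2.1, repeated in Protocol 1.2, gives the Period 2 entry as "Test) Itraconazole: 200 mg qd for 8 days + PF-07321332/ritonavir 300 mg/100 mg q12h x 3 days starting on Day 4". Itraconazole starts on Period 2 Day 1, so three itraconazole-only days sit under the Test label.
- **How AEs are tabulated.** SAP 8.3: "A set of summary tables split by treatment will be produced to evaluate any potential risk associated with the safety and toleration". SAP 8.3.4: "Adverse events will be reported in accordance with the sponsor reporting standards by treatment".

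Neither document states an exposure adjustment, an equal-length window, a separate follow-up column or a separate itraconazole-alone column for AEs.

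**The concern.** One secondary objective (SAP 2.2.2) is to describe the safety of PF-07321332/ritonavir without and with itraconazole. The by-treatment TEAE table is the natural place to look for that.

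In a randomised crossover, follow-up events would fall on whichever treatment came last, and that would differ between participants. Here nothing balances it: for anyone dosed in Period 2, the previous treatment during follow-up is the Period 2 treatment. The Test column therefore collects events over a longer time than the Reference column, and some of that time is itraconazole without PF-07321332/ritonavir. Even if itraconazole had no effect on tolerability, Test would be expected to show more events. With about 12 participants and few events, a reader of the table could not tell this from a drug effect.

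**Working it through.** **Inputs**

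- PF-07321332/ritonavir in Period 1: first dose Study Day 1 morning, fifth dose Study Day 3 morning (SAP 2.1).
- Period 2 starts on Study Day 5 (SAP 2.1), so Period 2 Day d is Study Day d + 4.
- Itraconazole: Period 2 Days 1–8, which is Study Days 5–12. PF-07321332/ritonavir: Period 2 Days 4–6, which is Study Days 8–10. Discharge: Period 2 Day 9, which is Study Day 13 (SAP 2.1, Protocol 4.1).
- Itraconazole is part of study intervention (Protocol 6), so the last dose is on Study Day 12 and the 28-day lag ends on Study Day 40.
- After discharge there is one planned contact, which may be by telephone, 28 to 35 days after the final dose (Protocol 1.3, Period 2 notes).

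**Check of the calendar.** The plan gives no AE window lengths, so I checked the day count against figures that it does give. Confinement from Day -1 to Study Day 13, with no Day 0, is 1 + 13 = 14 days and 13 nights, as Protocol 4.1 states. Total participation is 28 + 11 + (28 to 35) = 67 to 74 days, or 9.6 to 10.6 weeks, against a stated figure of about 10.

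**Windows for a participant who completes dosing**

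- Reference: 5 − 1 = 4 days.
- Test, inpatient: 13 − 5 = 8 days.
- Test, to the end of the lag: 40 − 5 = 35 days = 3 (itraconazole only) + 4 (first PF-07321332/ritonavir dose to 48 h after the fifth) + 1 (to discharge) + 27 (after discharge).

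**Ratio of Test to Reference.** Let c be the share of post-discharge events that are captured. With the itraconazole-only days in Test, as in the schema, the ratio is (8 + 27c)/4. With those days taken out it is (5 + 27c)/4.

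| c | Itraconazole-only days in Test | Itraconazole-only days taken out |
|---|---|---|
| 0 | 8/4 = 2.0 | 5/4 = 1.25 |
| 0.25 | 14.75/4 = 3.7 | 11.75/4 = 2.9 |
| 0.50 | 21.5/4 = 5.4 | 18.5/4 = 4.6 |
| 1 | 35/4 = 8.75 | 32/4 = 8.0 |

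The documents do not give c. The values 0.25 and 0.50 are assumptions.

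**Effect of early stopping.** A participant who stops in Period 1 carries follow-up events to Reference. Suppose 3 of 12 stopped after the Study Day 3 dose. Each would contribute Study Day 1 to Study Day 31 (3 + 28), or 30 days. Reference would then be 9 × 4 + 3 × 30 = 126 participant-days, or 10.5 per participant, and the full-capture ratio would fall to 35/10.5 = 3.3.

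**Illustration.** Assume a constant daily event rate r, equal in both treatments, with all 12 participants dosed in Period 2. These rates are not in the documents. Expected participants with at least one TEAE are 12 × (1 − exp(−r × days)).

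| r per day | Reference, 4 days | Test, 8 days | Test, 35 days |
|---|---|---|---|
| 0.5% | 0.24 | 0.47 | 1.93 |
| 1% | 0.47 | 0.92 | 3.54 |
| 2% | 0.92 | 1.77 | 6.04 |

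On inpatient days alone the gap is less than one participant at each of these rates. It becomes visible only as post-discharge capture rises.

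**Matched window.** First PF-07321332/ritonavir dose to 48 h after the fifth is Study Days 1 to 5 in Period 1 and Study Days 8 to 12 in Period 2, 4 days each, so the ratio is 1.0.

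**The case against.** The strongest reply is that nothing here is an error. The rule is explicit and reproducible, assigns late events to the last exposure, and fits the AE collection period of at least 28 days after the last dose (Protocol 8.3.1). The tables are descriptive: SAP 4.1 and 4.2 state no hypotheses and no decision rules. That stands, and it is a reason to keep the rule for the overall table. It does not make the rule suitable for a with/without description.

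Four stronger readings are tempting and go too far:

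- **That Test will show 8.75 times as many events.** That figure is a ratio of calendar days. As an event ratio it would need full capture from one planned contact and the same daily rate on undosed days after discharge as on dosing days. A reader might even run the window to a call on day 35 and get 7 + 35 = 42 days, since the follow-up sentence has no limit of its own. The TEAE definition before it stops at 28 days, so I take 35 as the maximum.
- **That the tables will contain no split.** SAP 8.3.4 defers to sponsor reporting standards that are not in the documents. One can say only that the SAP states none.
- **That the SAP contradicts itself on what Test is.** SAP 8.2 says "PF-07321332/ritonavir administered alone will be the Reference treatment and PF-07321332/ritonavir co-administered with itraconazole will be the Test treatment", which could suggest that Test starts on Period 2 Day 4. That sentence belongs to the PK model and does not define AE columns. The natural reading for AEs is the schema, with Period 2 Days 1–3 under Test. The mixing of itraconazole-alone events remains.
- **That the AE discontinuation summary has the same problem.** SAP 8.3.3 says "Participant discontinuations, temporary discontinuations or dose reductions due to adverse events will be detailed and summarized by treatment". Dosing ends on Study Day 12, so the 27 post-discharge days add almost nothing there. Only the itraconazole-only days matter.

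**Conclusion.** The point holds in a limited form. For participants dosed in Period 2, the stated rule and the schema build unequal observation time into the by-treatment TEAE summary, and nothing in the two documents offsets it. The size lies between 2:1 and 8.75:1 with the schema's definition of Test. It is lower if some participants stop in Period 1, and 1.25:1 on inpatient days if the itraconazole-only days are set apart. Where it falls rests on post-discharge capture, which the documents do not quantify.

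A reader might infer that the trial's safety conclusions or its main result are compromised. The documents do not support that. The effect is confined to a descriptive summary for one secondary objective; the primary PK comparison and the sample size do not use it. This is a cheap improvement, not a correction on which the trial depends.

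**What to change.** Keep the SAP 6.2.1 attribution for the overall TEAE listing and table. In SAP 6.2.1 and 8.3.4, add a split by onset:

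1. PF-07321332/ritonavir alone: from first dose to the first itraconazole dose or, for a participant who stops in Period 1, to 48 h after the last dose taken.
2. Itraconazole alone: from Period 2 Day 1 to the first Period 2 PF-07321332/ritonavir dose.
3. Combination: from that dose to discharge. A footnote should say that the last part is itraconazole without further PF-07321332/ritonavir, since Protocol 4.3 states: "Itraconazole will continue to be administered on Period 2, Days 7 and 8 to maintain maximal CYP3A4 inhibition until completion of PK sampling".
4. Follow-up: labelled by last treatment taken, so that Period 1 dropouts are not pooled unmarked with Period 2 participants.

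Base the with/without-itraconazole description on the matched 4-day window in each period. Events with later onset stay in the overall table, so none is lost. In SAP 8.3.3 only the itraconazole-alone split is needed.

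The cost is SAP and table-shell wording. AE onset is already recorded, so no new data are collected. The downside is a few more columns with sparse counts for about 12 participants. The matched window does not remove the confounding of period order with treatment, because Test always comes second; the report should say so.

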6.2.2. Laboratory Safety Tests

Safety laboratory tests will be performed as described in the protocol.

To determine if there are any clinically significant laboratory abnormalities, the haematological, clinical chemistry (serum) and urinalysis safety tests will be assessed against the criteria specified in the sponsor reporting standards. The assessment will take into account whether each participant's baseline test result is within or outside the laboratory reference range for the particular laboratory parameter.

Baseline is defined as the last pre-dose measurement taken in each study period.

6.2.3. Vital Signs Data

Supine measurements will be taken at times detailed in the Schedule of Activities given in the protocol.

Baseline is the last pre-dose recording in each study period.

The following vital signs endpoints will be determined:

- The minimum systolic and diastolic blood pressures and the minimum and maximum pulse rates over all measurements taken post-dose.
- The maximum increase and maximum decrease from baseline over all measurements taken post-dose for systolic and diastolic blood pressures.

The maximum increase from baseline will be calculated by firstly subtracting the baseline value from each post-dose measurement to give the change from baseline. The maximum of these values will then be selected, except in the case where a participant does not show an increase. In such an instance, the minimum decrease should be taken.

Similarly, the maximum decrease from baseline will be determined by selecting the minimum value of the changes from baseline. In cases where a participant does not show a decrease, the minimum increase should be taken.

